9.3.2.2.14 Infant Death

Infant death is defined as the death of an infant occurring between 12 and 52 weeks of life. In the event of an infant death, full pathological details will be requested, and any structural or congenital defects will be evaluated.

9.3.2.2.15 Maternal Death

Maternal death is defined as the death of a pregnant woman during pregnancy, labor, or delivery. Maternal deaths for up to 12 weeks after delivery will also be reported and full pathology details will be requested.

9.3.2.3 Information Collected from Consenting Patients and Healthcare Providers

The following variables will be collected during the study, as part of the local routine clinical practice, as available:

Baseline:

- Documentation of informed consent
- Reporter of information (patient, obstetrician, neurologist)
- Patient demographics and characteristics (e.g., age of mother and father, education level, race/ethnicity, height, weight, body mass index).
- Patient, secondary contact, and HCP contact information (obstetrician, neurologist, if possible)
- Lifestyle risk factors (e.g., smoking, caffeine consumption, alcohol use, illicit drug use)

- Current pregnancy information (e.g., LMP, gestational age, expected date of delivery [EDD], date and results of any prenatal tests)
- Maternal medical history:
 - Pregnancy history (e.g., parity, gravidity, previous preterm births, previous spontaneous abortions or elective or therapeutic terminations, reason for any elective or therapeutic termination, history of congenital malformations)
 - Surgical and medical history/significant maternal medications conditions other than MS (e.g., diabetes, high blood pressure)
 - MS disease history (including MS subtype and treatment history such as glatiramer acetate, disease duration, most recent Expanded Disability Status Scale [EDSS] score, if available)
 - Comorbid conditions
 - Family reproductive history (e.g., multiple births, congenital malformations, spontaneous abortions, premature births, chromosomal anomalies, developmental delays)
 - Family MS history
 - Ocrelizumab treatment (including start and stop dates, dose, dosing frequency, reason for discontinuation [if applicable])
 - Current and prior medication use from 6 months prior to conception (including other MS treatments such as glatiramer acetate, teratogenic medications, folic acid, other vitamins and supplements, vaccinations, medications to treat other chronic diseases)

Follow-up during pregnancy (during each trimester, approximately at 14, 21, and 34 weeks gestation):

- Date of contact
- Reporter of information (patient, obstetrician, neurologist)
- Changes in contact information (maternal, secondary contact, and HCP)
- Changes in pregnancy status:
 - Gestational age
 - Any prenatal testing performed and results (e.g., rubella titer, toxoplasmosis, venereal disease research laboratory test, hepatitis screen, ultrasounds, amniocentesis, maternal serum alpha-fetoprotein screen, glucose screen)
 - Pregnancy outcome, if applicable (e.g., elective or therapeutic termination, spontaneous abortion, ectopic pregnancy, molar pregnancy) as per [Section 9.3.2](#)

- Reason for elective or therapeutic termination (e.g., prenatal testing finding, risk to mother's health, undesired pregnancy), if applicable
 - Autopsy results and pathology reports, if available
- Changes in MS disease status (including treatment changes and relapses, EDSS score)
- Ocrelizumab treatment (including start and stop dates, dose, dosing frequency, reason for discontinuation [if applicable])
- Changes in comorbid conditions
- Current lifestyle factors (e.g., smoking, caffeine consumption, alcohol use, illicit drug use)
- Current medications (including other MS treatments such as glatiramer acetate, teratogenic medications or medication with potential fetal health implications, corticosteroids, folic acid, other vitamins and supplements, vaccinations, medications to treat other chronic diseases)
- SAEs related to pregnancy (as per [Section 11](#))

Birth outcome follow-up (approximately 4 weeks after EDD):

- Date of contact and date of pregnancy outcome or gestational age (in weeks)
- Changes in contact information; contact information for infant's HCP
- Reporter of information (patient, obstetrician, infant HCP)
- Pregnancy outcome (as per [Section 9.3.2](#), e.g., live birth, stillbirth, spontaneous abortion, elective or therapeutic termination):
 - Reason for elective or therapeutic termination (e.g., prenatal testing finding, risk to mother's health, undesired pregnancy), if applicable
 - Autopsy results and pathology reports, if available
- Mode of birth (vaginal delivery, assisted delivery/cesarean section, type of anesthesia)
- MS disease and treatment status since last follow-up
- Ocrelizumab treatment (including start and stop dates, dose, dosing frequency, reason for discontinuation [if applicable])
- Changes in comorbid conditions
- Current lifestyle factors (e.g., smoking, caffeine consumption, alcohol use, illicit drug use)
- Current medications (including other MS treatments such as glatiramer acetate, teratogenic medications or medication with potential fetal health implications, corticosteroids, folic acid, other vitamins and supplements, vaccinations, medications to treat other chronic diseases)

- Infant characteristics:
 - Gestational age at birth
 - Sex
 - Weight
 - Length
 - Head circumference
 - Birth order (for multiple births), and number of fetuses
 - Laboratory values, if available (e.g., CD19, neutrophil, lymphocyte, white blood cell, immunoglobulin and platelet counts)
 - Apgar scores (1, 5, and 10 minutes)
 - Congenital malformations noted (including description and attribution)
 - Vaccination information
 - Whether infant is breastfed
- SAEs related to pregnancy (as per [Section 11](#))
- All infant SAEs (including serious and severe infections of NCI CTCAE severity Grade 3, and hospitalizations other than for standard post-birth hospital stay)

Pediatric follow-up (approximately at 12, 26, and 52 weeks after birth):

- Reporter of information (patient, obstetrician, infant HCP)
- Infant characteristics:
 - Feeding behavior (including breastfeeding)
 - Weight
 - Length
 - Head circumference
 - Developmental milestones (e.g., social/emotional, language/communication, cognitive, movement/physical development milestones, as defined by the CDC [\[2016\]](#))
 - Laboratory values, if available (e.g., CD19, neutrophil, lymphocyte, white blood cell, immunoglobulin and platelet counts)
 - Evidence of any new congenital malformation since last follow-up
 - Vaccination information
 - All infant SAEs (including serious and severe infections of NCI CTCAE severity Grade 3, and hospitalizations other than for standard post-birth hospital stay)

Early termination of study participation contact, if applicable:

- Reporter of information (patient, obstetrician, infant HCP)
- Assessments appropriate for the time of withdrawal
- Reason for study withdrawal

- Ocrelizumab treatment (including start and stop dates, dose, dosing frequency, reason for discontinuation (if applicable))
- Other medications (including other MS treatments such as glatiramer acetate, teratogenic medications or medication with potential fetal health implications, corticosteroids, folic acid, other vitamins and supplements, vaccinations, medications to treat other chronic diseases)
- Pregnancy status:
 - Gestational age
 - Any prenatal testing performed and results (e.g., rubella titer, toxoplasmosis, venereal disease research laboratory test, hepatitis screen, ultrasounds, amniocentesis, maternal serum alpha-fetoprotein screen, glucose screen)
 - Pregnancy outcome, if applicable (per [Section 9.3.2](#), e.g., elective or therapeutic termination, spontaneous abortion, ectopic pregnancy, molar pregnancy)
 - Reason for elective or therapeutic termination (e.g., prenatal testing finding, risk to mother's health, undesired pregnancy), if applicable
 - Autopsy results and pathology reports, if available
- Infant characteristics (for live births):
 - Gestational age at birth
 - Sex
 - Weight
 - Length
 - Head circumference
 - Birth order (for multiple births), and number of fetuses
 - Laboratory values, if available (e.g., CD19, neutrophil, lymphocyte, white blood cell, immunoglobulin, and platelet counts)
 - Apgar scores (1, 5, and 10 minutes)
 - Congenital malformations noted (including description and attribution)
 - Whether infant is breastfed, if applicable
- SAEs related to pregnancy, pregnancy outcomes (as per [Section 11](#)) and/or infant SAEs (including serious and severe infections of NCI CTCAE severity Grade 3, and hospitalizations other than for standard post-birth hospital stay)

[Appendix 3](#) contains a more detailed review of data elements to be collected for this study.

9.4 DATA SOURCES

9.4.1 Collection of Data on the electronic Case Report Form

Patients' data obtained via questionnaires administered to patients or their HCPs will be recorded on eCRFs by the CC. The degree of detail and completeness of data collected is dependent on local clinical practice.

9.4.2 Data Collected during the Observation Period

After a patient provides consent, the CC will obtain demographic and contact information in addition to baseline information at the time of enrollment. All patient and HCP contact information will be confidential and will remain at the CC. The CC will then contact the patient each trimester to update contact information and ascertain the occurrence of pregnancy outcomes or other events (see [Section 9.3](#) for list of variables). Below is a list of the expected contacts with patients and HCPs:

Expected contacts with patient:

- Enrollment
- End of Trimester 1 (approximately 14 gestational weeks)
- Mid-Trimester 2 (approximately 21 gestational weeks)
- Mid-Trimester 3 (approximately 34 gestational weeks)
- EDD plus 4 weeks
- Birth plus 12 weeks, 26 weeks, and 52 weeks (live births only)

Expected contacts with the patient's HCP (neurologist, obstetrician):

- Enrollment
- Mid-Trimester 2 (approximately 21 gestational weeks)
- EDD plus 4 weeks

Expected contacts with the infant's HCP (live births only):

- EDD plus 4 weeks
- Birth plus 12 weeks
- Birth plus 26 weeks
- Birth plus 52 weeks

[figure not shown]
After a patient is enrolled, there will be at least three attempts made to contact the patient and/or the HCP via phone, e-mail, fax, and mail, as appropriate, approximately 10 business days apart. If data is obtained after a follow-up interval is passed, the CC will accept and enter the data and continue follow-up of the patient. If an HCP is not responsive at the time points described above, the patient will be asked to provide the information contained on the HCP worksheets. If the HCP then responds to contact, their information will supersede the patient-reported information. At all time points, the type of reporter (patient, obstetrician, neurologist, or infant HCP) will be recorded.

In the routine care setting, patients are seen regularly by their treating physicians either for treatment or for regular assessment after treatment. Thus, no study-specific visits or evaluations are required by this protocol.

If the patient experiences an adverse pregnancy outcome or has an elective or therapeutic termination or a termination of unknown cause, the HCP and patient will be encouraged to report the outcome to the CC as soon as possible. In the event of an elective or therapeutic termination, spontaneous abortion, fetal death or stillbirth, communications with the patients will cease after pregnancy outcome information has been obtained.

See [Figure 1](#) for data collection overview.

Figure 1 Data Collection Overview

See [Appendix 2](#) for the data collection overview (as per standard of care) during the treatment period.

9.4.3 Data Collected at Study Completion

All patients should have either the postpartum or the end of study data collection at 52 weeks postpartum (infant age 12 months), depending on the pregnancy outcome. The end of study data collection will also be completed if the patient discontinues from the study prematurely.

See [Appendix 2](#) for the data collection overview.

9.4.4 Loss to Follow-Up

For study purposes, patients will be considered lost to follow-up if any time-based assessment is missed and the corresponding data have not been received by the CC after making additional follow-up attempts using all contact methods available (e.g., phone, fax, registered letter; see [Section 9.4.2](#)). At least three attempts will be made up to 4 months after the expected date of the missed assessment. The case will be re-opened if additional information is later obtained. All HCPs and secondary contacts will also be contacted prior to considering a patient lost to follow-up. All data collected prior to the patient being lost to follow-up will be used for analyses, if possible. For analysis purposes, the date of discontinuation will be recorded as the date of last contact.

9.4.5 Safety Data Collection

Only SAEs related to pregnancy, pregnancy outcomes, and all infant SAEs through the first year of life are required to be recorded in the eCRF during the observation period. HCPs will report SAEs related to pregnancy, pregnancy outcomes, and infants to the CC who will enter them in the eCRF. See [Section 11](#) for a full description of safety procedures.

9.5 STUDY SIZE

The sample size for this study was calculated based on clinical, statistical, and practical considerations to determine the number of enrolled patients with pregnancies required to detect the prevalence of adverse pregnancy outcomes in the study and associated relative risk. Major congenital malformations are the primary outcome of interest for this study, and other outcomes are classified as secondary.

Assuming a 15% drop-out rate and a live birth rate of 62% ([FDA 2002](#); [Ventura et al. 2000](#)), 290 ocrelizumab-exposed pregnant women with MS will need to be enrolled to observe 153 pregnancy outcomes. This sample size provides 80% power to detect a relative risk of 2.5 or greater in major congenital malformations relative to the baseline prevalence of 3% in the external comparator ([CDC 2008](#)) at a significance level of $\alpha=0.05$ ([Table 2](#)). Should the actual live birth rate exceed 62%, fewer enrolled pregnant patients would be necessary to adequately power this study.

[Table 3](#) shows point estimates and 95% CIs for different hypothetical numbers of observed cases. With 153 pregnancy outcomes, an observed number of 14 major congenital malformations will give an estimated prevalence of 9% with 95% CI of (5.0%-14.7%), rejecting a relative risk of 1 when the baseline prevalence is 3%. Likewise, 18 major birth defects and 46 preterm births will reject a relative risk of 1 when the baseline prevalence is 4% and 10%, respectively.

In addition to the external comparator, the internal comparator group will enroll approximately 290 pregnant women to support the study objective to compare the maternal, fetal, and infant outcomes of women with MS who have not been exposed to

ocrelizumab before or during pregnancy. The internal comparator will provide supportive evidence to the comparison with the external comparator.

Table 2 Sample Size of Pregnancy Enrollment (Outcome) for 80% Power

Relative Risks	Number of Patients Exposed to Ocrelizumab for a Single Proportion Test when Comparing with an External Comparator	Number of Patients Exposed to Ocrelizumab for a Two Proportions Test when Comparing with an Internal Comparator with a 1:1 Allocation Ratio
2.0	602 (Pregnancy outcomes needed: 317)	1489 (Pregnancy outcomes needed: 785)
2.5	290 (Pregnancy outcomes needed: 153)	793 (Pregnancy outcomes needed: 418)

Note: Sample size is calculated using 2-sided exact test at $\alpha=0.05$ significance level. Sample sizes and power calculations are performed using PASS software, version 14. Assumptions: 3% baseline prevalence for major congenital malformations ^a, 15% drop-out rate, 62% live birth rate ^b.

^a CDC 2008

^b FDA 2002; Ventura et al. 2000

Table 3 95% Confidence Intervals for the Prevalence of Adverse Pregnancy Events Based on 153 Pregnancy Outcomes

Approximate Number of Adverse Pregnancy Events (Prevalence of Events) [95% Exact 2-Sided Clopper-Pearson Confidence Interval]		
3% (Major Congenital Malformations) ^a	4% (Major Birth Defects in Ocrelizumab-Exposed Patients) ^b	10% (Preterm Births) ^c
5 (3%) [0.9%, 7.1%]	6 (4%) [1.5%, 8.4%]	15 (10%) [5.7%, 15.9%]
9 (6%) [2.8%, 11.0%]	12 (8%) [4.2%, 13.5%]	31 (20%) [14.0%, 27.2%]
14 (9%) [5.0%, 14.7%]	18 (12%) [7.3%, 18.2%]	46 (30%) [22.9%, 37.9%]

^a CDC 2008

^b Ocrelizumab Investigator's Brochure 2016

^c Ferré et al. 2016

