9. RESEARCH METHODS

9.1 STUDY DESIGN

The design of the pregnancy exposure registry is consistent with relevant guidelines and recommendations ([FDA 2002](#); [European Medicines Agency 2005](#); [Gliklich et al. 2014](#); [Andrews et al. 2008](#)). This prospective observational registry will collect primary data from 290 ocrelizumab-exposed pregnant women (153 pregnancy outcomes) with MS and their healthcare providers (HCPs) from the United States, Germany, and other potential countries (see [Section 9.5](#)). Patients who have been exposed to ocrelizumab during the 6 months prior to their last menstrual period (LMP) or at any time during pregnancy are eligible for the ocrelizumab-exposed study group. Inclusion of exposures prior to LMP is based on the half-life and standard of care infusion schedule of ocrelizumab. Dosing and treatment duration of ocrelizumab as part of this non-interventional study are at the discretion of the physician in accordance with local clinical practice and local labeling.

The internal comparator group will consist of currently pregnant women with MS who were not exposed to any MS disease-modifying therapies (DMTs) during the 6 months prior to their LMP or at any time during pregnancy (apart from glatiramer acetate [e.g., Copaxone] exposure through the first trimester (for description and rationale, see [Section 9.7.2.1](#)). Internal comparator patients will be enrolled from the same sites as the ocrelizumab-exposed women and follow the same study procedures for follow-up and data collection. Women will be eligible in the internal comparator group if they fall into one of the following categories:

- Pregnant women with MS with documentation that the patient was not exposed to any MS DMTs during the 6 months prior to their LMP or at any time during their pregnancy
- OR
- Pregnant women with MS with documentation that the patient was exposed to glatiramer acetate during the 6 months prior to their LMP through the first trimester

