9.7.1 Methods of Analysis

Demographic information (e.g., age, race/ethnicity, body mass index [BMI]), clinical characteristics, and other potential factors that may affect pregnancy outcome will be described. Descriptive statistics (i.e., mean, SD, median, minimum, and maximum) will be provided for continuous variables. Counts and percentages will be provided for categorical variables. The number of patients with non-missing data will be presented.

Prenatal exposure to ocrelizumab will be summarized based on the timing of exposure by trimester. Total duration of exposure will be calculated using the start date of ocrelizumab use and the stop date +6 months.

The prevalence of spontaneous abortions will be calculated by dividing the number of fetal losses occurring before 20 weeks gestation by the total number of pregnancies. Spontaneous abortions defined as occurring before 22 weeks gestation will also be examined in a sensitivity analysis to account for global variation in the definition for this outcome. Prevalence per 100 pregnancies along with 95% CIs will be presented.

The prevalence of congenital malformations will be calculated using Metropolitan Atlanta Congenital Defects Program (MACDP) and EUROCAT conventions. The total prevalence will be calculated by dividing the number of cases of each event (observed in live births, fetal deaths, elective or therapeutic terminations, and at any gestational age) by the total number of births (stillbirths + live births). The prevalence *at birth* will be

calculated as number of cases observed in live births and stillbirths divided by the total number of births (stillbirths + live births). Prevalence per 100 births along with 95% CIs will be presented.

Prevalence of preterm birth and small for gestational age will be calculated by dividing the number of cases by the total number of births (stillbirths + live births). Prevalence per 100 births and corresponding 95% CIs will be presented.

For growth and developmental delays, the prevalence will be calculated as the number of cases divided by the total number of live births. Prevalence per 100 live births and 95% CIs will be calculated.

Exact 95% CIs including Clopper-Pearson CI for binomial proportion will be assessed.

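### The sample-size target of 153 counts expected live births but is labelled as pregnancy outcomes, of which 290 women would give at least about 247

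*Protocol*

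**What the plan says.** Section 9.5 starts from "Assuming a 15% drop-out rate and a live birth rate of 62" per cent and concludes that 290 exposed women "will need to be enrolled to observe 153 pregnancy outcomes". Section 9.1 repeats the pairing as "290 ocrelizumab-exposed pregnant women (153 pregnancy outcomes", and the synopsis does the same. Table 2 labels its cells in the same way, for example "290 (Pregnancy outcomes needed: 153", "602 (Pregnancy outcomes needed: 317" and "793 (Pregnancy outcomes needed: 418"; its fourth cell pairs 1489 women with 785. The title of Table 3 ends "Based on 153 Pregnancy Outcomes".

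Section 9.5 adds that a live birth rate above 62% would reduce the number of women to be enrolled.

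Elsewhere the term is broader. The eligibility criteria (Sections 9.2.2.1 and 9.2.2.2) treat the outcome of a pregnancy as either a loss or a live birth. The birth follow-up items in the synopsis list live birth, stillbirth, spontaneous abortion and termination under it. Section 11.1.1.1 also brings in ectopic and molar pregnancy.

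Section 9.7.1 uses two denominators. Spontaneous abortions are divided "by the total number of pregnancies". Malformations, preterm birth and small for gestational age are divided by births, meaning stillbirths plus live births.

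**The concern.** A count that has been multiplied by a live birth rate is a count of live births. Calling it pregnancy outcomes gives the target a unit that the protocol itself defines more widely, so the stated target and its derivation do not agree.

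Two things depend on the unit. The first is recruitment. Section 9.5 allows enrolment to fall below 290 and Section 9.1.1.2 tracks recruitment against projections, so the team needs to know what is being counted. Counting losses and terminations towards 153 would leave too few births for the primary outcome. The second is the per-pregnancy outcomes. Spontaneous abortion is a named objective and a planned comparison, and a reader who takes 153 as the number of pregnancies with an outcome will think its estimate less precise than it should be.

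**Working it through.** **Inputs.** Drop-out 15%, live birth rate 62%, baseline prevalence 3%, relative risk 2.5 (3% to 7.5%), two-sided alpha 0.05, 80% power: all from Section 9.5 and the note to Table 2. Stillbirth prevalence 7.6 to 8.0 per 1000: Section 9.7.2.2.2.

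**1. Reproduce Table 2.** Women enrolled = n / (0.85 x 0.62) = n / 0.527.

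| Count in Table 2 | n / 0.527 | Stated enrolment | n / 0.85 |
|---|---|---|---|
| 153 | 290.3 | 290 | 180.0 |
| 317 | 601.5 | 602 | 372.9 |
| 418 | 793.2 | 793 | 491.8 |
| 785 | 1489.6 | 1489 | 923.5 |

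All four stated enrolments match n / 0.527, allowing for rounding. None matches n / 0.85, which would apply if the count included every kind of outcome. All four counts are therefore live births.

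**2. Pregnancy outcomes expected from 290 women.**
- If all drop-out happens before the pregnancy ends: 290 x 0.85 = 246.5, about 247.
- If all drop-out happens after the pregnancy ends: 290. Section 9.4.4 counts a woman as lost when any scheduled assessment is missed and cannot be recovered, follow-up runs to 52 weeks after birth, and data collected before the loss are kept.
- The range is therefore 247 to 290.

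**3. Base of Table 3.** Its columns are major congenital malformations, major birth defects and preterm births, which are all per-birth outcomes. Adding stillbirths at 7.6 to 8.0 per 1000 births gives 153 / (1 - 0.008) = 154.2, about 154. So 153 is in effect the right base, and 247 would be wrong there.

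**4. If the label were taken literally.** 153 outcomes of any kind x 0.62 = 94.9, about 95 live births, reached at 153 / 0.85 = 180 women. Exact binomial power, equal-tailed two-sided test, 7.5% against 3%:
- n = 153: rejects at 10 or more cases (upper tail 0.0176 under 3%); power 71.8%.
- n = 95: rejects at 7 or more cases (upper tail 0.0245 under 3%); power 57.5%.

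The normal approximation that reproduces the protocol's 153 is [1.960 x sqrt(0.03 x 0.97) + 0.842 x sqrt(0.075 x 0.925)]^2 / 0.045^2 = 152.7. On that scale power goes from 80% at 153 to about 65% at 95. The loss is about 14 to 15 points either way.

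**5. Per-pregnancy precision.** The protocol gives no planning rate for spontaneous abortion, so 10% to 20% is assumed. Clopper-Pearson 95% intervals:

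| Assumed rate | On 153 | On 247 |
|---|---|---|
| 10% | 15 events: 5.6% to 15.7% | 25 events: 6.7% to 14.6% |
| 15% | 23 events: 9.8% to 21.7% | 37 events: 10.8% to 20.1% |
| 20% | 31 events: 14.2% to 27.5% | 49 events: 15.1% to 25.4% |

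**The case against.** The strongest reply is that this is loose terminology with no numerical effect. The intended unit can be recovered from the same paragraph, because a higher live birth rate lowers the required enrolment only if live births are being counted. A team following that sentence would count births. At 290 women the label changes neither power nor the primary calculation. All of this stands, and it limits the point to a correction of labels.

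Two stronger readings are tempting, and the documents support neither. A reader might infer that the registry closes at 153 pregnancy outcomes and so ends with 95 births. No section says so: Section 9.5 requires 290 women, Section 9.1.3 ends the study at the last data from the last subject, and Section 10.1.3 has no rule based on an outcome count. A reader might also infer that the intervals in Table 3 rest on the wrong base. They do not, because none of its three columns is a per-pregnancy outcome.

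Two smaller objections also stand. The protocol states no planned precision for spontaneous abortion, so no stated figure is wrong there, and reading it from 153 errs on the cautious side. The figure of 247 is a lower bound, since it places all drop-out before the pregnancy ends.

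What the reply does not remove is that the target as written, in five places, contradicts both its own derivation and the protocol's use of the term. A reader should not have to infer the unit of a sample-size target.

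**Conclusion.** The point holds as a labelling error. The counts 153, 317, 418 and 785 are expected live births. On the protocol's assumptions of 15% drop-out and a 62% live birth rate, 290 women give 153 live births and between about 247 and 290 pregnancies with a known outcome, depending on when drop-out occurs.

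Enrolment of 290, the primary calculation and the numbers in Table 3 are not affected by the label. The fall to about 95 live births and about 57.5% exact power is what would follow if 153 outcomes of any kind were used as the recruitment target. It is a risk created by the label and not a planned result. The gap between 71.8% and the protocol's 80% at n = 153 has a different cause (a normal approximation where the note to Table 2 names an exact test) and is not part of this point.

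The correction should be made, because it concerns the unit of the target for the primary outcome and costs almost nothing.

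**What to change.** - In the synopsis, Section 9.1, Section 9.5, all four cells of Table 2 and the title of Table 3, replace pregnancy outcomes with live births for these counts.
- In Section 9.5, state that recruitment, and any reduction in enrolment below 290, is judged against 153 live births.
- In Section 9.5, add that 290 women are expected to give about 247 or more pregnancies with a known outcome, and that per-pregnancy outcomes such as spontaneous abortion will rest on that number.
- Leave the base and the figures of Table 3 as they are; only the title changes.

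The cost is a wording change. No extra women, data or analyses are needed, and enrolment stays at 290.

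### The 80% power claimed for a relative risk of 2.5 comes from a normal approximation; under the exact test the protocol names, 153 outcomes give about 72%.

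*Protocol*

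**What the plan says.** Section 9.5 and the Study Size part of the synopsis give one power statement for the primary outcome: "This sample size provides 80% power to detect a relative risk of 2.5 or greater in major congenital malformations". The setting is a single proportion against an external comparator, with 290 women enrolled, 153 outcomes observed and alpha 0.05. The note to Table 2 states the method, "Sample size is calculated using 2-sided exact test", and the assumption "3% baseline prevalence for major congenital malformations". The enrolment figure is derived by "Assuming a 15% drop-out rate and a live birth rate of 62" percent.

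Table 3 lists exact two-sided Clopper-Pearson intervals for 153 outcomes. In the 3% column it prints 5 events with 0.9% to 7.1%, 9 events with 2.8% to 11.0%, and 14 events with 5.0% to 14.7%. The text of Section 9.5 uses the 14-event interval as an example of a result that rejects a relative risk of 1. Section 9.7.1 plans exact intervals, including Clopper-Pearson, for the reported prevalences.

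**The concern.** An exact binomial test on rare events usually needs more observations than the large-sample formula. A size that equals the large-sample result but is labelled exact may therefore fall short of its stated power. Table 3 points the same way, since the interval at three times the 3% column's smallest percentage is clear of 3% but the one at twice that percentage is not.

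This is the only power claim for major congenital malformations, in a registry run to meet part of a postmarketing requirement. If it is too high, readers will take a registry that does not exclude 3% as stronger reassurance against a 2.5-fold risk than it is.

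**Working it through.** **Inputs** (Section 9.5 and the note to Table 2): baseline p0 = 0.03; p1 = 2.5 × 0.03 = 0.075; n = 153; two-sided alpha 0.05, so 0.025 per tail; target power 80%.

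**1. Reproducing the plan's figure.** Normal approximation for one proportion:

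n = [(1.96·√(p0(1−p0)) + 0.8416·√(p1(1−p1))) / (p1−p0)]²

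- RR 2.5: [(1.96 × 0.1706 + 0.8416 × 0.2634) / 0.045]² = [(0.3344 + 0.2217) / 0.045]² = 152.7, rounded up to 153. The approximate power at 153 is 80.06%.
- RR 2.0 (p1 = 0.06): the same formula gives 317.1; Table 2 prints 317.

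Both single-proportion entries of Table 2 match this formula. Others tried for RR 2.5 do not: one-sided normal 124.6, two-sided normal with continuity correction 174.2, two-sided arcsine 183.8.

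**2. The exact test named in the note, n = 153.**

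| Events | P(X ≥ events) at 3% | Two-sided p, doubled tail | Two-sided p, minimum likelihood | Clopper-Pearson lower limit | Excludes 3%? |
|---|---|---|---|---|---|
| 9 | 0.0420 | 0.084 | 0.051 | 2.72% | No |
| 10 | 0.0176 | 0.035 | 0.027 | 3.18% | Yes |

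The equal-tailed test, the minimum-likelihood test and the Clopper-Pearson interval all need at least 10 events.

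- Power at 7.5%: P(X ≥ 10) = 71.8%.
- Counting 9 events as a rejection would give P(X ≥ 9) = 81.8%, but 9 is outside the rejection region.
- Solving P(X ≥ 10) = 0.80 for the prevalence and dividing by 0.03 gives a relative risk of 2.70.

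**3. Exact sizes, for information.** Exact power is saw-toothed in n, and the size depends on which exact test is meant.

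- Equal-tailed: power first reaches 80% at n = 181, falls below again after 185, and stays at or above 80% from 196.
- Minimum likelihood: power reaches 80% at n = 151, fails at 152 and 153, holds over 166 to 178, and stays at or above 80% from 196.

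**4. Table 3.** The printed intervals belong to unrounded counts, that is, 153 times the heading percentage, not to the integers printed.

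| Printed count | Printed interval | Count that reproduces it | Interval for the printed integer |
|---|---|---|---|
| 5 | 0.9% to 7.1% | 4.59 | 1.1% to 7.5% |
| 9 | 2.8% to 11.0% | 9.18 | 2.7% to 10.9% |
| 14 | 5.0% to 14.7% | 13.77 | 5.1% to 14.9% |

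Whether 3% is included is the same either way in all three rows.

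**5. What the 153 are.** 290 × 0.85 = 246.5 women with a known outcome; 246.5 × 0.62 = 152.8 expected live births.

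**The case against.** The strongest defence is that the synopsis bases the external comparisons on point estimates and 95% intervals, with no inductive inference, so no pass/fail test is planned and its power matters little. This bears on weight but does not remove the error. Section 9.5 makes the power claim, and itself reads an exact interval as rejecting a relative risk of 1. The intervals to be reported are exact, so exact power describes what they can show.

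A second defence is that part of the shortfall is discreteness: under the minimum-likelihood test, n = 151 would give just over 80%. That is true, and it is why a single replacement size should not be quoted without naming the test. At the protocol's own n of 153, both exact versions give 71.8%.

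Third, the exact label is not wrong throughout Table 2. In the two-proportion column, 418 per group for RR 2.5 has about 80.7% power with Fisher's exact test. For RR 2.0 in the single-proportion column, 317 gives 79.5% with the minimum-likelihood test, although 71.7% with the equal-tailed test. The clear failure is the RR 2.5 single-proportion entry, which is the one the registry is sized on.

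The Table 3 differences are also small, and its heading calls the event numbers approximate.

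**Conclusion.** The point holds. With 153 outcomes, a 3% baseline and the two-sided exact test named in the protocol, power for a relative risk of 2.5 is about 72%, some 8 percentage points below the stated 80%; 80% is reached at a relative risk of about 2.7. This rests only on the protocol's own inputs and treats 3% as a fixed reference value, as the protocol does.

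Three stronger readings are not supported:

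- A reader might infer that the plan treats 9 malformations as enough to exclude 3%. It does not: Table 3 prints an interval for 9 events that contains 3%, and the text claims rejection only at 14.
- A reader might recompute power at the European prevalences quoted elsewhere in the protocol and call the result a further shortfall. The claim is expressly conditional on 3%, so such figures are sensitivity results, not errors in the plan.
- A reader might take the 153 as all pregnancy outcomes, leaving far fewer live births and much lower power. Section 9.5's own multiplication by the live birth rate rules this out; only the label is loose.

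**What to change.** In Section 9.5 and the synopsis, state that 153 outcomes give about 72% exact power for a relative risk of 2.5 against 3% (at least 10 malformations needed), or 80% for a relative risk of about 2.7. In the Table 2 note, say that the single-proportion column uses a normal approximation. If exact sizes are added for information, name the exact test and note the saw-tooth: equal-tailed power first reaches 80% at 181, and both exact versions stay at or above 80% from 196.

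Minor corrections in the same section:

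- Recompute the Table 3 intervals on the printed integer counts, and the 14-event interval repeated in the text. No conclusion changes.
- Describe the 153 as expected live births, and note that the malformation denominator in Section 9.7.1 is live births plus stillbirths.

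The cost is wording and table edits only. Enrolment, outcome and analysis stay as they are; the stated power becomes less favourable.
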